3.1. Description of Overall Study Design and Plan

This study is a single arm, open-label, Phase II trial. There will be two phases in this study, the run-in phase and the continuation phase (Phase II). Phase II will consist of 2 stages.

Run-in Phase

During the run-in phase, three patients will be enrolled and will receive 3 cycles of i.v. administration of SCB01A at a dose of 3.25 mg/m^2 on Days 1 and 8 of each cycle in a 3-week cycle (Dose 1). If one of the three patients experienced a Dose Limiting (DLT) during the first 3 cycles, an additional three patients will be enrolled at the same dose level (Dose 1). If ≤ 1 of subjects experienced DLT at the given dose level, the dose of the subsequent cohort will be increased to the next level, then this process will continue until $\geq 2/3$ or $2/6$ of subjects experience DLT at certain dose level or the maximum dose(Dose 4) in this protocol, 24 mg/ m^2 is reached.

Rules for dose escalation for the run-in phase of the study are listed as following:

1. If 0/3 subjects have a DLT, escalate to the next higher dose level with a cohort of three subjects, unless the maximum dose to be tested in this study, i.e. 24 mg/m^2 (Dose 4). If 0/3 subjects have DLT in a cohort of 24 mg/m^2 (Dose 4), the 24 mg/m^2 (Dose 4) will be determined as the Optimal Dose.
2. If 1/3 subjects have DLT(s), enrol three more subjects at the same dose level:
 - a) If the dose for the cohort is less than 24 mg/m^2 (Dose 4) and 1/6 subjects have DLT(s), escalate to the next higher dose level;
 - b) If the dose for the cohort is higher than 3.5 mg/m^2 (Dose 1) and $> 1/6$ subjects have a DLT, de-escalate to the next dose level (0a, 1a, 2a or 3a) with 3 subjects .
 - c) If > 1 out of 6 subjects in the next lower dose (0a, 1a, 2a or 3a) have DLT(s), then the previous dose will be defined as the MTD.
 - d) If ≤ 1 out of 6 subjects in the next lower dose (0a, 1a, 2a or 3a) have DLT(s), then that dose will be defined as the Optimal Dose.
3. If the dose for the cohort is 24 mg/m^2 (Dose 4) and $1 \leq 6$ subjects have a DLT, then the dose level of 24 mg/m^2 (Dose 4) will be determined as the Optimal Dose.

Patients enrolled in the run-in phase must either complete 3 cycles of study treatment or experience a DLT to be included in the Full Analysis Set (FAS) for statistical analyses. During the run-in phase, patients who do not complete the 3 cycles of study treatment, and do not experience a DLT, will be replaced.

Phase II (The continuation phase)

After the Optimal Dose was determined in the run-in phase, a total number of 13 patients (including patients received Optimal Dose in the run-in phase) will be enrolled for stage 1 to receive 3 cycles of i.v. administration of SCB01A at Optimal Dose.

A safety committee review will be performed after stage 1 with the patients who completed 3 cycles of SCB01A treatment at the Optimal Dose. If more than two disease controls (DCs) are observed, another 21 patients will be enrolled into Stage 2 at the same dose level.

No patients will be replaced in the continuation phase (Phase II).

[figure not shown]

Figure 2: Schematic Study Design

All patients will be treated until occurrence of progressive disease, intolerable adverse events (AEs)/toxicity, consent withdrawal or death. After discontinuation of study treatment, all patients will be followed for survival and disease-specific therapies of the clinician's choice. Follow-up visits will be scheduled every 3 weeks for 9 weeks, thereafter every 9 weeks until the end of the study.

The study will be terminated 36 weeks after the last patient has received their 1st treatment with SCB01A.

Safety monitoring committee:

A safety monitoring committee will be established to:

- Evaluate all AEs, and safety laboratory data for the run-in phase;

- Decide on the recommended dose regimen of SCB01A for Phase II.

The schedule of assessments for the run-in phase and Phase II, stages 1 and 2 is shown in detail in Table 1 and Table 2, respectively. The results of protocol specific assessments and procedures will be recorded in the source documents for the patients and on the appropriate page of the electronic case report form (eCRF). The different study days are described below.

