During the run-in phase, three patients will be enrolled and will receive 3 cycles of i.v. administration of SCB01A at a dose of 3.25 mg/m² (Dose 1) on Days 1 and 8 of each cycle in a 3-week cycle (Dose 1). If 1 of the three patients experiences a dose limiting toxicity (DLT) during the first 3 cycles, an additional three patients will be enrolled at the same dose level. If 0/6 or 1/6 i.e. ≤ 1 of subjects experienced DLT at the given dose level, the dose of the subsequent cohort will be increased to the next level, then this process will continue until $>1/6$ of subjects experience DLT at certain dose level or the maximum dose in this protocol, 24 mg/m² (Dose 4) is reached.

Patients enrolled in the run-in phase must either complete 3 cycles of study treatment or experience a DLT to be included in the Full Analysis Set (FAS) for the statistical analyses. During the run-in phase, patients who do not complete the 3 cycles of study treatment, and who do not experience a DLT, will be replaced.

Rules for dose escalation for the run-in phase of the study are listed as following:

1. Dose level will start at 3.25 mg/m² (Dose 1) in the 1st Cohort and can be escalated to 12 mg/m² (Dose 2), 18 mg/m² (Dose 3) and 24 mg/m² (Dose 4). If ≤ 1 subjects have DLT in a cohort of 24 mg/m² (Dose 4), the 24 mg/m² (Dose 4) will be determined as the Optimal Dose.
2. If $=1/3$ subjects in a cohort have DLT(s), enrol three more subjects at the same dose level or if ≤ 1 subjects (i.e., 0/3 or 1/6) experience DLT then subjects can be enrolled into the next higher dose level as per below:
 - a) **Dose Level 3.25 mg/m² (Dose 1):** This dose level has been completed as part of protocol amendment #2 and ≤ 1 patient experienced DLT. Patients will be enrolled in the next dose level based on results from 3.25 mg/m² (Dose 1) Cohort.
 - b) **Dose Level 12 mg/m² (Dose 2):** If 1 patient experiences DLT then 3 additional patients to be enrolled in the same dose level. If the total DLT from 6 patients at the same dose level is ≤ 1 , then the study to move to the next higher dose level. If >1 patients have DLT, then 3 patients to be enrolled at the reduced dose of 10 mg/m² (Dose 1a).

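### Section 3.1's numbered run-in rules contradict themselves and the synopsis at the reduced doses (0a, 1a, 2a, 3a)

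*Protocol*

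**What the plan says.** The planned ladder is in the synopsis: dosing starts at 3.25 mg/m² (Dose 1) "in the 1st Cohort and can be escalated to" 12, 18 and 24 mg/m² (Doses 2, 3 and 4). SAP Section 2.1 gives the same ladder. Doses 0a, 1a, 2a and 3a (5, 10, 15 and 21 mg/m²) are fallbacks, opened only after a higher dose has failed.

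Section 3.1 of the protocol gives numbered rules:

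- Rule 1: "If 0/3 subjects have a DLT, escalate to the next higher dose level with a cohort of three subjects", with an exception only for Dose 4.
- Rule 2(a), after expansion to six, for any dose below 24 mg/m²: "1/6 subjects have DLT(s), escalate to the next higher dose level".
- Rule 2(b), for more than 1/6 DLTs above Dose 1: "de-escalate to the next dose level (0a, 1a, 2a or 3a) with 3 subjects".
- Rule 2(c), for more than 1 of 6 at any reduced dose: "then the previous dose will be defined as the MTD".
- Rule 2(d), for at most 1 of 6 at any reduced dose: "then that dose will be defined as the Optimal Dose".

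The paragraph above these rules ends escalation when at least 2/3, or 2/6, "of subjects experience DLT at certain dose level or the maximum dose(Dose 4) in this protocol" is reached.

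The synopsis sets the rules out dose by dose. Under rule b, if Dose 2 has more than 1 DLT, "then 3 patients to be enrolled at the reduced dose of" 10 mg/m² (Dose 1a). Rules f and h do the same from Dose 3 to 2a and from Dose 4 to 3a. Rules c, d, f and h make a reduced dose with at most 1 DLT the Optimal Dose. Under rule c, more than 1 DLT at Dose 1a leads to Dose 0a.

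**The concern.** One result at a reduced dose can carry two different instructions. After 1/6, rule 2(a) escalates and rule 2(d) stops. After 0/3, rule 1 escalates while the synopsis stops. The escalation would go to a dose that has already shown 2 or more DLTs. After failure at Dose 1a, rule 2(c) ends the search with an MTD, while the synopsis tries 5 mg/m² first.

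Finding the Optimal Dose is the run-in's primary objective, and Phase II patients are treated at that dose. Section 4.8 refers dose selection and timing to Section 3.1, not to the synopsis, and the reviewed text does not say which governs. What is at stake is whether a passing reduced dose ends the search, and whether 5 mg/m² is tested after 10 mg/m² fails.

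**Working it through.** **1. The plan's own figure.** The synopsis states a run-in maximum of 30. Following synopsis rules a-h along every path, the longest is Doses 1, 2, 3, 4, 3a with six patients each: 5 × 6 = 30, which matches. Other end points need at most 24 (ending at Dose 4, 2a or 0a) or 18 (ending at 1a). Section 3.1 read literally can return from a reduced dose to the dose above it, so its rules do not by themselves give this cap. That supports the synopsis as the intended scheme.

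**2. Rules side by side at a reduced dose.**

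| Result | Section 3.1, numbered rules | Synopsis |
|---|---|---|
| 0/3 | Rule 1: escalate | Optimal Dose |
| 1/6 | 2(a): escalate; 2(d): Optimal Dose | Optimal Dose |
| 2 or more of 6, at 1a | 2(c): MTD; 2(b) lists 0a as a next level | Go to 0a |
| 2 or more of 6, at 0a, 2a, 3a | 2(c): MTD | MTD is Dose 1, 2, 3 respectively |
| 2/3 or 3/3 | No numbered step | Same action as for 2 or more of 6 |

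On the ladder, the next level up is 12 mg/m² from 0a or 1a, 18 from 2a and 24 from 3a. Each must already have had 2 or more DLTs, or the reduced dose would not have been opened. Rule 2(d) does not cure the 0/3 row, because it sits under the 1/3 trigger and counts out of six. The last row of 2(c) agrees with the synopsis only if the previous dose means the next lower ladder dose. Rule 2(b)'s listing of 0a has a purpose only if failure at 1a leads there, so 2(b) and 2(c) also disagree at 1a.

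**3. How often a contested result would arise.** The documents give no DLT rate for the Day 1 and Day 8 schedule. Assume a common rate p of 10%-50% at the planned and reduced doses. The cuts 12 to 10, 18 to 15 and 24 to 21 mg/m² are only 17%, 17% and 13% (1 − 10/12, 1 − 15/18, 1 − 21/24), so similar rates are plausible. Given that the planned dose is opened:

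- P(0/3) = (1−p)³
- P(1/6) = 3p(1−p)⁵
- P(2/3 or 3/3) = 1 − (1−p)³ − 3p(1−p)²
- P(rejected) = P(2/3 or 3/3) + 3p(1−p)²[1 − (1−p)³]

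| p | P(rejected) | rejected, then 1/6 | rejected, then 0/3 | rejected twice | 2/3 or 3/3 in first three |
|---|---|---|---|---|---|
| 0.1 | 0.094 | 0.017 | 0.068 | 0.009 | 0.028 |
| 0.2 | 0.291 | 0.057 | 0.149 | 0.085 | 0.104 |
| 0.3 | 0.506 | 0.077 | 0.173 | 0.256 | 0.216 |
| 0.4 | 0.691 | 0.064 | 0.149 | 0.477 | 0.352 |
| 0.5 | 0.828 | 0.039 | 0.104 | 0.686 | 0.500 |

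For example, at p = 0.3 rejected then 0/3 is 0.5057 × 0.343 = 0.173. The rejected-twice column applies to Dose 2 followed by Dose 1a.

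**4. Sensitivity to equal rates.** With 33.3% at the planned dose and 23.3% at the reduced dose, the figures are 10.6% (then 1/6), 25.8% (then 0/3) and 20.8% (rejected twice).

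**The case against.** The strongest reply is that nobody reading the whole protocol would be misled. Escalation is said to end once 2 or more DLTs occur, and reduced doses open only after that. Rule 2(d) names the reduced doses expressly and can be taken as the specific rule overriding 2(a). The synopsis covers 0/3 plainly. The safety committee meets after each run-in cohort and decides on escalation, so no cohort opens mechanically. Figures 1 and 2 are not shown in the reviewed text and may make the scheme clear.

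Much of this stands: the intent is recoverable, and this is an inconsistency of drafting, not a design choice. It does not remove the conflict. The specific-rule reading does not reach 0/3 within Section 3.1, and it does nothing for 2(c) at Dose 1a. Committee review is a safeguard but does not say which written rule applies.

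A reader might also infer that the protocol has no rule for 2/3 or 3/3 DLTs. The documents do not support that. The Section 3.1 preamble stops escalation there, and synopsis rules b, f and h give the next step without requiring six patients. The numbered rules merely fail to restate it.

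A reader might further assume DLT rates of a third or more, which would raise the lower limits for rejection at both doses and for 2/3 or 3/3. Nothing in the documents justifies leaving out lower rates. Section 1.2 reports 5 DLTs with 33 phase I subjects (5/33 = 15%). That is only a rough guide, because it comes from mixed doses given once every three weeks. At 15% for both doses, Dose 2 and Dose 1a would both be rejected 3.5% of the time, and 2/3 or 3/3 would occur 6.1% of the time.

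**Conclusion.** The concern holds as an inconsistency in Section 3.1 that should be corrected. Two conflicts are established from the text alone: rules 1 and 2(a) against 2(d) and the synopsis when a reduced dose passes, and rule 2(c) against synopsis rule c (and the listing in 2(b)) when Dose 1a fails. The missing restatement for 2/3 or 3/3 is secondary.

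At assumed equal DLT rates of 10%-50%, the chance of reaching each contested outcome is about 2%-8% (rejected, then 1/6), 7%-17% (rejected, then 0/3) and 1%-69% (Doses 2 and 1a both rejected). For 2/3 or 3/3 in the first three at a planned dose it is 3%-50%. The ranges are wide because the rate is unknown.

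It would be tempting to read these as chances of wrong dosing, or to conclude that patients were sent back to a rejected dose. Neither follows. The committee could apply the synopsis in every case, and SAP Section 2.1 reports recruitment only at Doses 1 and 2 before termination, so no reduced-dose cohort was affected.

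**What to change.** Align Section 3.1 with the synopsis:

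- **Rules 1 and 2(a).** Limit rule 2(a), and only the escalation sentence of rule 1, to Doses 1, 2 and 3 on the ladder 3.25, 12, 18, 24 mg/m².
- **Dose 4.** Keep rule 1's second sentence, and keep rule 3 reworded as at most 1 of 6, so that Dose 4 with 0/3 or 1/6 DLTs remains the Optimal Dose. Limiting the whole of rule 1 to Doses 1-3 would delete the 0/3 case.
- **Reduced doses.** State that a reduced dose with 0/3 or 1/6 DLTs is the Optimal Dose, with no re-escalation.
- **Rule 2(b).** Make it stand alone: 2 or more DLTs, in three or six patients, at Dose 2, 3 or 4 opens Dose 1a, 2a or 3a respectively.
- **Rule 2(c).** 2 or more DLTs at Dose 1a opens Dose 0a; 2 or more at Dose 0a, 2a or 3a makes Dose 1, 2 or 3 respectively the MTD.

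The cost is amendment wording only, with no added patients or procedures. With the trial terminated, the practical value is in correcting the rules before the text is reused.

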 - c) **Dose level 10 mg/m² (Dose 1a):** If 1 patient experiences DLT then 3 additional patients to be enrolled in the same dose level. If ≤ 1 patient has DLT then dose level 10mg/ m² (Dose 1a) will be considered Optimal Dose. If >1 patients have DLT then dose will be further reduced to 5 mg/m² (Dose 0a) for the next 3 patients enrolled in the study.

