	
d) Dose level 5 mg/m² (Dose 0a): If 1 patient experiences DLT then we enrol 3 additional patient in the same dose level. If ≤ 1 has patient DLT then dose level 5 mg/m² (Dose 0a) will be considered Optimal Dose. If >1 patients have DLT then 3.5 mg/m² (Dose 1) will be considered MTD.
 
e) Dose Level 18 mg/m² (Dose 3): If 1 patient experiences DLT then we enrol 3 additional patient in the same dose level. If the total DLT from 6 patients in the same dose level is ≤ 1 then we move to the next higher dose level.
 
f) Dose Level 15 mg/m² (Dose 2a): If >1 patient have DLT in Dose 3, then 3 patients to be enrolled at a reduced dose of 15mg/ m² (Dose 2a). If 1 patient experiences DLT then 3 additional patients to be enrolled in the same dose level. If ≤ 1 patient has DLT then dose level 15mg/ m² (Dose 2a) will be considered Optimal Dose. If >1 patients have DLT then 12 mg/m² (Dose 2) will be considered MTD.
 
g) Dose Level 24 mg/m² (Dose 4): If 1 patient experiences DLT then 3 additional patients to be enrolled in the same dose level. If the total DLT from 6 patients at the same dose level is ≤ 1 then Dose Level 24 mg/m² (Dose 4) will be the Optimal Dose.
 
h) Dose Level 21mg/m² (Dose 3a): If >1 patient has DLT in Dose 4, then 3 patients to be enrolled at reduced dose of 21mg/ m² (Dose 3a). If 1 patient experiences DLT then 3 additional patient to be enrolled in the same dose level. If ≤ 1 patient has DLT then dose level 21mg/ m² (Dose 3a) will be considered Optimal Dose. If >1 patients have DLT then 18 mg/m² (Dose 3) will be considered MTD.
 
Phase II : In the phase II of the study additional patients will be enrolled to evaluate the Optimal Dose as established by review of the safety committee.
 
Stage 1: In stage 1 of phase II, 7 subjects will be enrolled and dosed at the optimal dose level as established by the safety review committee. Note: In case only 3 patients were enrolled in the optimal dose cohort of the run-in phase then 10 patients will be enrolled in stage 1 thus enrolling total 13 subjects in the optimal dose level.
 
Stage 2: Once all subjects have completed their treatment cycle in stage 1 then a review by safety committee will be conducted to confirm if stage 2 can be initiated. If confirmed then stage 2 of the study will enrol additional 21 subjects who will be dosed at the same Optimal Dose level identified for stage 1
 
No patients will be replaced in the continuation phase (Phase II).

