--	---

[figure not shown]

Figure 1: Schematic Study Design

All patients will be treated until the occurrence of progressive disease, intolerable adverse events (AEs)/toxicity, consent withdrawal or death. After discontinuation of study treatment, all patients will be followed for survival and disease-specific therapies of the clinician's choice will be administered. Follow-up visits will be scheduled every 3 weeks for 9 weeks, thereafter every 9 weeks until the end of the study.

The study will be completed 36 weeks after the last patient has received their 1st treatment with SCB01A.

Dose Limiting Toxicity (DLT) definition (in run-in phase)

- All toxicities will be classified according to the National Cancer Institute (NCI) Common Terminology Criteria for AEs (CTCAE) version 4.03. DLT will be defined as the occurrence of any of the following criteria unless there is definitive alternative evidence that administration of SCB01A did not cause the specific toxicity:
 1. Grade 4 neutropenia exceeding 5 days duration;
 2. Grade 4 thrombocytopenia;
 3. Grade 4 anemia;
 4. Grade 3 or greater neutropenia with complications (e.g., fever, infection, etc.);
 5. Grade 3 or greater thrombocytopenia with complications (e.g., bleeding);
 6. Grade 3 or greater non-hematological AEs including Grade 3 unmanageable nausea and vomiting that persist for 3 or more days after drug administration. Grade 3 fatigue lasting for ≤1 week is not considered as a DLT;
 7. Grade 3 or greater prolonged QTc interval;
 8. Grade 3 or greater neurotoxicity;
 9. Delayed treatment is exceeding 14 days duration due to drug-

	
related toxicity.
 
Safety Monitoring Committee (SRC)
 
The SRC, composed of the principle investigators at each participating site, an independent medical monitor (physician experienced in oncology studies), and medical and safety representatives of the Sponsor, will be responsible for making decisions regarding dose escalation, determining the recommended dose, and starting enrollment of cohort expansions. Serial assessments of PK results also may be taken into account for the determination of the MTD and Optimal Dose.
 
Safety Monitoring Committee will meet after completion of Each Cohort in the Run-in Phase and after the completion of Phase II stage 1.
 
MTD Definition
 
The MTD is defined as the dose immediately preceding the dose level at which DLTs are observed in 2 or more patients.

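### Section 3.1 rule 2(c) wrongly includes Dose 1a: failure at 10 mg/m² makes an unnamed previous dose the MTD, where the synopsis and rule 2(b) call for 3 patients at Dose 0a (5 mg/m²)

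*Protocol*

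**What the plan says.** The run-in steps up through Dose 1 (3.25 mg/m²), Dose 2 (12), Dose 3 (18) and Dose 4 (24). The fallback doses are 0a (5), 1a (10), 2a (15) and 3a (21). Protocol Section 4.8 lists all eight in ascending order.

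**Protocol Section 3.1.**
- Rule 2(b) covers a cohort above Dose 1 with more than 1 of 6 DLTs. It instructs the site to "de-escalate to the next dose level (0a, 1a, 2a or 3a) with 3 subjects".
- Rule 2(c) covers more than 1 of 6 DLTs at a fallback dose: "in the next lower dose (0a, 1a, 2a or 3a) have DLT(s), then the previous dose will be defined as the MTD".
- The opening run-in paragraph also counts failure in a cohort of three: "then this process will continue until $\geq 2/3$ or $2/6$ of subjects experience DLT at certain dose level".

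**Protocol synopsis, Study Design.**
- Item (c), Dose 1a: "If >1 patients have DLT then dose will be further reduced to 5 mg/m² (Dose 0a"), with the next 3 patients enrolled there.
- Item (d), Dose 0a: "If ≤ 1 has patient DLT then dose level 5 mg/m² (Dose 0a) will be considered Optimal Dose". With more than 1 DLT at 0a, Dose 1 is the MTD.
- Item (f), Dose 2a: "If >1 patients have DLT then 12 mg/m² (Dose 2) will be considered MTD".
- Item (h), Dose 3a: "If >1 patients have DLT then 18 mg/m² (Dose 3) will be considered MTD".
- MTD Definition: "The MTD is defined as the dose immediately preceding the dose level at which DLTs are observed in 2 or more patients".

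SAP Section 2.1 says that testing could continue at a reduced level and lists the four fallback doses. It does not say what follows failure at 1a.

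**The concern.** The run-in's primary objective is to determine the optimal dose. After failure at Dose 2 and then at Dose 1a, the protocol gives two different instructions. The synopsis opens 5 mg/m² and may make it the Optimal Dose. Rule 2(c) declares an MTD at that point and does not say which dose it is.

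The synopsis reaches Dose 0a only through failure at 1a. If rule 2(c) governs 1a, Dose 0a has no way in, although rules 2(b) to 2(d), Section 4.8 and Table 1 all carry it. A committee following rule 2(c) could leave 5 mg/m² untested, or could record as the MTD a dose that was never given on this schedule or one that had already failed.

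**Working it through.** The plan states no figure for this branch, so there is none to reproduce. The check has two parts: a comparison of the rules, and the chance of reaching the branch.

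**1. More than 1 DLT at each fallback dose**

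| Failed dose | Synopsis | Section 3.1 rule 2(c) |
|---|---|---|
| 0a (5) | MTD = Dose 1 | MTD = previous dose |
| 1a (10) | 3 patients at 0a | MTD = previous dose |
| 2a (15) | MTD = Dose 2 | MTD = previous dose |
| 3a (21) | MTD = Dose 3 | MTD = previous dose |

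Only at 1a does the synopsis continue de-escalation where rule 2(c) sets an MTD.

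**2. What the previous dose could mean**

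| Reading | after 0a | after 1a | after 2a | after 3a |
|---|---|---|---|---|
| Next lower main dose | Dose 1 | Dose 1 (cleared) | Dose 2 | Dose 3 |
| Next lower level in the full list | Dose 1 | Dose 0a (untested) | Dose 2 | Dose 3 |
| Dose given just before | Dose 1a | Dose 2 (failed) | Dose 3 | Dose 4 |

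The first two readings agree with synopsis items (d), (f) and (h), so those items cannot choose between them. The third disagrees with those items, which counts against it, but the wording of rule 2(c) does not exclude it. The MTD definition does not settle the matter, because a preceding dose can be preceding in order or in time. On every reading, the result after 1a differs from the synopsis step.

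**3. Chance of the branch once Dose 2 is open**

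The inputs are the 3+3 rule from the synopsis and Section 3.1, and a DLT probability p that is assumed. Section 1.2 reports only 5 DLTs in a phase I study that enrolled 33 patients, with no rate by dose for dosing on Days 1 and 8.

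- P(pass a level) = (1−p)³ + 3p(1−p)⁵, and P(fail) = 1 − P(pass). For p = 0.2: 0.512 + 0.6 × 0.32768 = 0.7086, so P(fail) = 0.2914.
- P(branch) = P(fail at 12) × P(fail at 10). For p = 0.2 at both: 0.2914² = 0.0849.
- Rules 2(b) and 2(c) both speak of six patients and sit under the case of 1 DLT in the first three. If only that kind of failure counts, P(fail in six) = 3p(1−p)² × [1 − (1−p)³]. For p = 0.2: 0.384 × 0.488 = 0.1874. Applied at both doses: 0.1874² = 0.0351.

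| p at 12 and 10 mg/m² | P(fail) | Branch | P(fail in six) | Branch, six-patient wording at both doses |
|---|---|---|---|---|
| 0.1 | 0.0939 | 0.9% | 0.0659 | 0.4% |
| 0.2 | 0.2914 | 8.5% | 0.1874 | 3.5% |
| 0.3 | 0.5057 | 25.6% | 0.2897 | 8.4% |
| 0.4 | 0.6907 | 47.7% | 0.3387 | 11.5% |

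With a lower rate at 10 mg/m², the full 3+3 rule gives:
- 0.2 then 0.1: 0.2914 × 0.0939 = 2.7%
- 0.3 then 0.2: 0.5057 × 0.2914 = 14.7%
- 0.4 then 0.3: 0.6907 × 0.5057 = 34.9%

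**The case against.** The best defence is that the protocol answers the question elsewhere. Synopsis item (c) is specific to Dose 1a and explicit, and a dose-by-dose rule is a better guide than a four-item list in parentheses. Rule 2(b) covers 1a in general terms and lists 0a as a target. Rule 2(c) defines an MTD and does not say that enrolment stops. The safety committee decides the Phase II dose (Section 3.3), and MTD and Optimal Dose are separate terms. The dose schematics (Figures 1 and 2) were not available to me and may show the intended step.

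Most of this stands, and it indicates that the synopsis is what was meant. It does not make rule 2(c) correct. That rule lists 1a by name and gives a different consequence for the same event.

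Three stronger inferences are tempting, and the documents do not support them.
- A reader might infer that the protocol would settle on 3.25 instead of 5 mg/m², a ratio of 5/3.25 = 1.54. That takes the previous dose to be Dose 1, which the text does not establish. Rule 2(c) also does not set the Phase II dose.
- A reader might infer that the error always falls towards a lower, cleared dose and so cannot add toxicity risk. This rests on the same single reading. The opposite inference, that the rule would send patients to the failed 12 mg/m², rests on the reading that fits the synopsis least well.
- A reader might infer that dosing in the trial was affected. SAP Section 2.1 says that only the 3.25 and 12 mg/m² cohorts were recruited before termination.

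**Conclusion.** The inconsistency is real and is in current text. Dose 1a does not belong in rule 2(c), and the MTD that the rule would declare after 1a is unnamed and open to three readings. None of the three matches the synopsis, and two would call an untested or a failed dose the MTD. This holds without any assumption about toxicity.

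How often the branch would arise does rest on assumption. With equal DLT rates of 0.1 to 0.4 at 12 and 10 mg/m², it runs from 0.9% to 47.7% under the full 3+3 rule. It runs from 0.4% to 11.5% if the six-patient wording is applied at both doses. No document supports one value within these ranges.

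The point is minor. The branch was not reached, the synopsis gives a workable instruction, and the correction is editorial. It would matter if this escalation scheme were reused.

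**What to change.** 1. In Section 3.1, limit rule 2(c) to Doses 0a, 2a and 3a.
2. State in Section 3.1 that more than 1 DLT at Dose 1a, whether in 3 or in 6 patients, leads to 3 patients at Dose 0a, as in synopsis item (c).
3. In rule 2(c), replace the unnamed previous dose with Dose 1 after 0a, Dose 2 after 2a and Dose 3 after 3a.
4. Align the synopsis MTD definition with these named doses.

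The cost is wording only. The 3 to 6 patients at Dose 0a are already allowed by the synopsis. The path through Doses 1, 2, 1a and 0a needs at most 4 × 6 = 24 patients before replacements, within the planned run-in maximum of 30.

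### Protocol Section 3.1 does not give one consistent action for the reduced-dose cohorts (0a, 1a, 2a, 3a) of the run-in phase; the synopsis dose-by-dose rules do.

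*Protocol*

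**What the plan says.** Protocol Section 3.1 lists these rules for the run-in phase:

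- Rule 1: "If 0/3 subjects have a DLT, escalate to the next higher dose level with a cohort of three subjects". The only exception is Dose 4 (24 mg/m²).
- Rule 2 applies when 1 of 3 patients has a DLT. The cohort is expanded to 6, and (a) to (d) follow beneath it.
- 2(a), any cohort below 24 mg/m²: "and 1/6 subjects have DLT(s), escalate to the next higher dose level".
- 2(b), any cohort above Dose 1 with more than 1/6: "subjects have a DLT, de-escalate to the next dose level (0a, 1a, 2a or 3a) with 3 subjects".
- 2(c), a reduced dose with more than 1 of 6: "have DLT(s), then the previous dose will be defined as the MTD".
- 2(d), which makes a reduced dose the Optimal Dose with at most one DLT: "out of 6 subjects in the next lower dose (0a, 1a, 2a or 3a) have DLT(s), then that dose will be defined as".

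The lead paragraph above these rules lets escalation continue until 2/3 or 2/6 "of subjects experience DLT at certain dose level or the maximum dose(Dose 4) in this protocol" is reached.

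The synopsis has a general rule that with 0/3 or 1/6 "experience DLT then subjects can be enrolled into the next higher dose level as per below", and then treats each dose separately. For at most one DLT at 10 mg/m², rule (c) ends with "Dose 1a) will be considered Optimal Dose". Rules (d), (f) and (h) say the same for 0a, 2a and 3a. When a reduced dose fails, 1a leads to 0a, and 0a, 2a and 3a lead to Dose 1, 2 and 3 as the MTD.

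**The concern.** A reduced dose is opened only after at least 2 patients had a DLT at the dose above it. The rules should then say plainly whether a tolerated reduced dose goes forward to Phase II, and what follows if it also fails. Section 3.1 leaves three situations open: 0/3 at any reduced dose, 1/6 at any reduced dose, and more than 1 DLT at Dose 1a.

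A site or committee member working from Section 3.1 alone could treat 3 more patients at a dose that has already failed. After a failed Dose 1a, the same reader could stop and name an MTD where the synopsis calls for 0a to be tested.

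**Working it through.** **Step 1. Which level is next above each reduced dose.** The doses in mg/m² are 3.25 (Dose 1), 5 (0a), 10 (1a), 12 (Dose 2), 15 (2a), 18 (Dose 3), 21 (3a) and 24 (Dose 4). The next level above 1a, 2a and 3a is Dose 2, 3 and 4 respectively, which is the dose whose failure opened it. Above 0a the next level is 1a or, counting main doses only, Dose 2. Dose 0a is opened only after both of those have failed, so the result is the same on either count.

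**Step 2. The rules side by side, as printed.**

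| Result at a reduced dose | Section 3.1 | Synopsis |
|---|---|---|
| 0/3 | Rule 1 only: escalate. 2(c) and 2(d) need 1/3 first and count out of 6 | Optimal Dose |
| 1/6 | 2(a): escalate; 2(d): Optimal Dose | Optimal Dose |
| More than 1 of 6 at 1a | 2(b): open 0a; 2(c): MTD at the previous dose | Open 0a |

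In the last row the previous dose is not named. In order of testing it is Dose 2, which failed. In order of dose it is 0a, which is untested.

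**Step 3. The plan's own patient count.** The longest path under the synopsis is Doses 1, 2, 3, 4 and 3a at 6 patients each: 5 × 6 = 30. This equals the stated run-in maximum of 30, before replacements. A literal return to Dose 4 after 1/6 at 3a would add 3 to 6 patients, giving 33 to 36.

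**Step 4. Illustrative outcome probabilities.** These are ordinary 3+3 probabilities, conditional on a reduced dose being open. The true DLT rate p is an assumption, because the documents give no rate by dose for this schedule. Section 1.2 reports 5 DLTs among 33 phase I subjects, but that pools doses given once every 3 weeks and does not settle p. With q = 1 − p:

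- 0/3: q³
- 1/6: 3pq² × q³
- failure after expansion to 6: 3pq² × (1 − q³)
- 2 or more DLTs in the first 3: 3p²q + p³

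| p | 0/3 | 1/6 | Fails after expansion | 2 or more in first 3 |
|---|---|---|---|---|
| 0.10 | 0.729 | 0.177 | 0.066 | 0.028 |
| 0.20 | 0.512 | 0.197 | 0.187 | 0.104 |
| 0.30 | 0.343 | 0.151 | 0.290 | 0.216 |
| 0.40 | 0.216 | 0.093 | 0.339 | 0.352 |
| 0.50 | 0.125 | 0.047 | 0.328 | 0.500 |

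At p = 0.20, for example, 0.512 + 0.197 + 0.187 + 0.104 = 1.000. For Dose 1a, the clash between 2(b) and 2(c) read literally (out of 6) is the fourth column. If 2(c) is also taken to cover 2 or more DLTs in the first 3, the last two columns add to 0.094, 0.291, 0.506, 0.691 and 0.828.

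**The case against.** The strongest reply is that the intended path can be recovered from the documents. The lead paragraph of 3.1 ends escalation at 2/3 or 2/6, and a reduced dose is opened only after that point. At 1/6, rule 2(d) names the reduced doses and is the more specific rule; applying 2(a) instead would leave it almost no purpose. The synopsis settles every case by dose. Its own opening paragraph also escalates at 0/6 or 1/6 without excluding reduced doses, so 3.1 should not be read more strictly than the synopsis. The safety committee decides on escalation and meets after each cohort. Figure 2 belongs to Section 3.1, was not readable in the text available, and may show the path.

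Most of this stands. A reader might infer that the protocol intends to send patients back to a failed dose; the lead paragraph and 2(d) do not support that. A reader might also infer from 2(c) that a failed Dose 3 or 4 could be named the MTD after 2a or 3a fails. The synopsis defines the MTD as the dose just below the level with 2 or more DLTs, and its rules (f) and (h) name Dose 2 and Dose 3, so that reading should be set aside. Nor do the probabilities measure harm. They take no account of the chance that a reduced dose is opened, or of the DLTs already seen just above it.

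Three gaps remain. No listed rule in 3.1 gives the alternative action at 0/3. Rules 2(a) and 2(d) do contradict each other as printed. The MTD definition does not rescue 2(c) at Dose 1a, because there the dose just below is the untested 0a.

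**Conclusion.** The inconsistency is real and minor. It is a drafting fault in a safety-critical list, and it does not show that re-escalation was intended. Section 3.1 is silent or contradictory at 0/3, at 1/6 and after a failed Dose 1a, where the synopsis is definite.

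If a reduced dose had been opened with a true DLT rate of 20%, about 71% of such cohorts (0.512 + 0.197) would have met the 0/3 gap or the 1/6 contradiction. That figure rests wholly on the assumed rate and on a reduced dose being open. SAP Section 2.1 reports that only Doses 1 and 2 were recruited, so no patient was affected.

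**What to change.** Limit rules 1 and 2(a) to Doses 1, 2 and 3, leaving Dose 4 its own statement. Replace 2(b) to 2(d) with rules placed outside the 1/3 condition. Merely adding 0/3 to 2(d) where it stands would not work, because that condition would still exclude it. A single table used in both the synopsis and Section 3.1 is the cleanest form:

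| Dose level | DLTs / evaluable patients | Action |
|---|---|---|
| 2, 3 or 4 | 2 or more in 3 or 6 | Open 1a, 2a or 3a respectively |
| 0a, 1a, 2a or 3a | 1/3 | Enrol 3 more at the same dose |
| 0a, 1a, 2a or 3a | 0/3 or 1/6 | That dose is the Optimal Dose |
| 1a | 2 or more in 3 or 6 | Go to 0a |
| 0a, 2a or 3a | 2 or more in 3 or 6 | MTD is Dose 1 (3.25 mg/m²), Dose 2 or Dose 3 respectively |

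The cost is protocol wording only. These are the synopsis rules, so the longest path stays at 30 patients before replacements. As the trial ended during the run-in phase, the change matters for any restart or reuse of this design.
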